To investigate this secondary objective, we will correlate degree and intensity of uptake of ⁶⁸Ga-DOTATATE with subsequent progression of disease, being determined by standard of care whole body bone scans (43) and CT/MR imaging (44), as well as clinical parameters. We will utilize 6 and 12 month progression free survival outcomes within the context of our one year funding mechanism, and believe these parameters are realistic for this patient population. However, as it is likely that some of the patients will not have evidence of progression until after completion of our funding mechanism, patients will be consented to be followed until there is clinical evidence of progression. To the best of our knowledge, there are no studies that have investigated ⁶⁸Ga-DOTATATE uptake in patients who have recently become castration resistant nor evaluated the correlation between the level of ⁶⁸Ga-DOTATATE uptake and treatment outcome with oral agents (abiraterone acetate or enzalutamide). This study will use standard of care, well-defined and accepted measures of progression free survival, to correlate with uptake on an initial ⁶⁸Ga-DOTATATE PET as a surrogate for degree of neuroendocrine transdifferentiation. This study will not be utilizing a follow-up ⁶⁸Ga-DOTATATE PET for therapy response.

C. Study design and methods

[figure not shown]
Experimental design. We will undertake a study with 20 patients who have castration resistant metastatic prostate carcinoma with skeletal and/or nodal and/or visceral involvement. The patients will serve as their own control. We will perform a Ga-68 DOTATATE PET-CT of the whole body as per the detailed protocol below (Objective 1). Prior to the Ga-68 DOTATATE PET-CT, all patients will undergo conventional staging including ^{99m}Tc MDP bone scanning and CT or MR within 90 days which are standard of care at our institution. This study will not interfere with standard patient evaluation or delay therapy. Other imaging may also be obtained clinically.

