The patients will be also followed up in the context of this study (per clinical routine) for at least one-year post-therapy to determine if the degree of Ga-68 DOTATATE uptake correlates with progression free survival of disease as evidence by imaging progression, PSA progression, clinical progression, which defined by investigator and mortality (Objective 2). It is expected that higher Ga-68 DOTATATE uptake will lead to a shorter time to progression with discrete foci of uptake greater than liver being defined as positive for enhanced receptor expression, and thus indicative of malignancy.

C.1 Ga-68 DOTATATE radiolabeling

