established. However, based on literature examples (30), a diagnosis of high Ga-68 DOTATATE uptake will be assigned to lesions with a SUVmax ≥ 8 , moderate Ga-68 DOTATATE uptake will be assigned to lesions with a SUVmax ≥ 5 , and mild Ga-68 DOTATATE uptake will be assigned to lesions with uptake greater than liver and/or SUVmax ≥ 3 .

- 4) In addition, the measurements above will be supplemented by the following from RECIST 1.1 Criteria (44).

C.6 Comparison to Ga-68 DOTATATE uptake with standard response criteria

For response criteria to oral agents, patients will serve as their own controls.

- 1) Ga-68 DOTATATE PET-CT uptake will be correlated with clinical response criteria including time to PSA progression, which is defined as the time from initiation of treatment to the date of earliest objective evidence of PSA progression, which will be assessed at each clinic visit, and is defined as time from initiation of treatment to the date of PSA absolute increase ≥ 2 ng/mL and $\geq 25\%$ above nadir or baseline values confirmed by a second consecutive value obtained at least 3 weeks later or death due to any cause. Repeat imaging during treatment will obtain per clinician discretion such as when any sign of clinical progression or PSA progression. Radiological progression of bone lesions will be determined by using Prostate Cancer Working Group 3 (PCWG3) recommendations for clinical trial conduct in castration resistant disease and radiographic progression of soft tissue lesions will be determined by using modified RECIST 1.1 criteria.

We will utilize 6 and 12 month progression free survival outcomes and patients will be consented to be followed until there is any evidence of progression.

C.7 Follow up

This will be done as part of routine standard of care without special visits required of the patient. Clinical visits will be determined by clinician's discretion as will be ordering of laboratory tests including CBC, CMP, testosterone and PSA. Within one year after Ga-68 DOTATATE PET-CT imaging (or earlier if progression), imaging response to therapy using standard criteria including repeat CT or MR, bone scan and PSA will be obtained. Accrual goals will be 4 patients every year for a total of 20 patients in 5 years.

D. Patient selection

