Patients will be recruited from the Genitourinary Medical Oncology clinic at Winship Cancer Institute per the inclusion and exclusion criteria below. It is estimated that a minimum of 20 patients per month who meet inclusion criteria are seen in the Genitourinary Medical Oncology clinic at Winship Cancer Institute. However, if we do not enroll our target goals, patients with mCRPC from Georgia Cancer Center for Excellence at Grady will be referred to this study as [name] also staffs that genitourinary oncology clinic.

Inclusion Criteria:

- 1) Patients must be 18 years of age or older.
- 2) Patients with metastatic castration resistant prostate carcinoma with skeletal, visceral and/or nodal involvement.
- 3) Ability to lie still for PET scanning

- 4) Patients must be able to provide written informed consent

Written consent will be obtained from the patient prior to the PET scan day and documented. Eligibility checklist will be verified with the patient prior to the scan day once consent is obtained.

Procedures:

PET Scan Day

- Obtain written informed consent if not earlier obtained.
- Inclusion/exclusion criteria review if not earlier done.
- Medical history and medication review if not earlier done.

E. Statistical Analysis

Patient baseline characteristics and degree of ⁶⁸Ga-DOTATATE uptake will be summarized using descriptive statistics. The inter-rater agreement will be assessed by Kappa statistics or intra-class correlation coefficient. The degree of uptake will be plotted against length of time to progress, and the association will be described by Spearman correlation coefficient with 95% confidence interval (CI). In addition, we will dichotomize degree of uptake by median and define it as high vs. low, and apply Wilcoxon rank sum test or Fisher exact test wherever appropriate. The association with progression free survival will be able to describe by Kaplan-Meier method along log-rank p-value (due to the small sample size, this may not be feasible). This is a pilot study with main goal to evaluate the feasibility, and no statistical power is possible.

F. Adverse Events

An adverse event is defined as any untoward medical occurrence associated with the use of a drug in humans whether or not considered drug-related.

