G. Data and Safety Monitoring Plan (DSMP):

Patients will be monitored by the technologists and study nurse before and after whole body Ga-68 DOTATATE PET-CT examination for any adverse events/reactions per clinical routine. They will be given contact phone numbers to call if they experience any problems (i.e. problems with the IV site, any allergic reaction symptoms). They will be followed routinely by their referring oncologist with clinical exams, and the PI will work with the co-investigators and referring physicians to ensure that the patients continue to follow up as scheduled.

The Data and Safety Monitoring Committee (DSMC) of the Winship Cancer Institute will also oversee the conduct of this study (every 6 months or annually – depending on the risk level of the protocol). This committee will review pertinent aspects of study conduct including patient safety, compliance with protocol, data collection and efficacy. The committee will review the charts of 10% of patients enrolled to the study and two of the first 5 patients entered to the study. The Committee reserves the right to conduct additional audits if necessary. The Principal Investigator (PI) or designee is responsible for notifying the DSMC about the accrual of patients when the first 5 have been entered to the study.

It should be kept in mind that this patient cohort typically has a median survival of 18 months and it is of much greater probability that an SAE may occur and be related to the patient's natural disease progression and/or therapy. Only those SAE's related to the radiotracer Ga-68 DOTATATE itself will be reported as part of this trial as the therapy itself is not considered experimental.

H: Pharmaceutical, biologic, and device information

Radiation Dosimetry. The study will be approved by not only the Emory IRB but also the Radiation Safety Committee. The maximum number of PET studies a patient will receive in one year is 1 Ga-68 DOTATATE study.

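### Objective 2 rests on a Spearman correlation with time to progression, with no data cut and no rule for patients who have not progressed

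*Combined protocol and SAP*

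**What the plan says.** Section E gives the main description of Objective 2: "The degree of uptake will be plotted against length of time to progress, and the association will be described by Spearman correlation coefficient", with a 95% confidence interval. It then splits uptake at the median and says it will "apply Wilcoxon rank sum test or Fisher exact test wherever appropriate", without naming the outcome for either test. Kaplan-Meier is listed for progression-free survival "along log-rank p-value (due to the small sample size, this may not be feasible".

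Other sections bear on how complete the times will be:

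- **B. Objectives (rationale):** "it is likely that some of the patients will not have evidence of progression until after completion of our funding mechanism". The same sentence goes on to say that patients consent to follow-up until progression.
- **C. Study design and methods:** patients are followed "for at least one-year post-therapy to determine if the degree of Ga-68 DOTATATE uptake correlates with progression free survival".
- **C.6, on follow-up to progression:** "We will utilize 6 and 12 month progression free survival outcomes and patients will be consented to be followed until there is any evidence".
- **C.7:** "Accrual goals will be 4 patients every year for a total of 20 patients in 5 years".

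No section says when the analysis is run, or what value a patient without progression takes in the Spearman or Wilcoxon analysis.

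**The concern.** Spearman's coefficient has no mechanism for censored times. An analyst with some non-progressors has at least three options: drop them, use their last follow-up as if it were progression, or tie them at a common cut. Dropping them removes the longest times, which are the informative end of the scale if the study hypothesis is right. The plan does not choose among these. It also casts doubt on the one listed method that would make the choice unnecessary.

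The caveat may be meant only for the log-rank p-value. On either reading, 20 patients limit power but do not prevent the calculation.

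The association between uptake and progression is the whole of the secondary objective. The opening summary says the results may be used to design larger studies, so a correlation that depends on an unstated choice could be carried into that design work.

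**Working it through.** The plan has no power or event calculation to reproduce. Its accrual figure is consistent (4 × 5 = 20), but it is not a derivation of sample size.

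**Inputs from the documents:** n = 20; 4 entries a year for 5 years; at least one year of follow-up; mortality counts as an event (Section C); median survival of 18 months (Section G).

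**Assumptions, because the documents give no figures:** uptake standard normal; proportional hazards with HR 2 per SD; exponential times; median time to progression 8, 12 or 16 months; no dropout.

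**Follow-up scenarios.**

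1. Accrual over 60 months with an assumed cut at month 72. Follow-up then runs from 72 - 60 = 12 months to 72 - 0 = 72 months.
2. A common cut at 12 months for each patient.
3. Everyone followed to progression.

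**Expected non-progressors at a 12-month cut.** The share is S(12), the average over uptake x of exp(-λ₀ · 2^x · 12), with λ₀ set so that S(median) = 0.5. At median 12, S(12) = 0.5 and 20 × 0.5 = 10.0.

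**Mean Spearman correlation by simulation** (4,000 runs per setting; the uncensored value is about -0.47 throughout):

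| Scenario and quantity | Median 8 | Median 12 | Median 16 |
|---|---|---|---|
| (1) Censored, of 20 | 2.3 | 3.8 | 5.1 |
| (1) Non-progressors dropped | -0.38 | -0.33 | -0.30 |
| (1) Last follow-up used as progression | -0.46 | -0.44 | -0.43 |
| (1) Runs where the two differ by 0.1 or more | 36% | 51% | 57% |
| (1) Runs where all 20 have progressed | 8% | 1% | 0.3% |
| (1) Censored C-index | 0.67 | 0.67 | 0.68 |
| (2) Censored, of 20 | 7.6 | 10.0 | 11.7 |
| (2) Non-progressors dropped | -0.21 | -0.15 | -0.11 to -0.14 |
| (2) Non-progressors tied at 12 months | -0.44 | -0.41 | -0.38 |
| (2) Runs where the two differ by 0.2 or more | 56% | 62% | 65% |
| (2) Censored C-index | 0.68 | 0.68 | 0.68 |

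Independent repeats agree within about 0.03, and the one range in the table is the spread across repeats. In scenario (3) there is no bias. With a Weibull shape of 1.5, all 20 have progressed by the month-72 cut in 34%, 7% and 1% of runs.

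**Other effect sizes, median 12.**

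- HR 1.5: uncensored -0.29; scenario (1) -0.20 dropped and -0.28 last follow-up; scenario (2) -0.08 dropped and -0.24 tied.
- HR 3: uncensored -0.63; scenario (1) -0.47 and -0.60; scenario (2) -0.28 and -0.56.

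**Sampling error for comparison.** By Fisher's z, atanh(0.47) = 0.510 and 1.96/√17 = 0.475. The limits are tanh(0.985) = 0.76 and tanh(0.035) = 0.03, so the 95% CI around -0.47 is about -0.76 to -0.03.

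**Is log-rank feasible at n = 20?** Log-rank and Cox returned a result in at least 99.5% of simulated data sets. Power is low. Schoenfeld's formula is Φ(√d/2 · ln 2 - 1.96) for a between-group HR of 2 and d events. With d = 20 it gives Φ(1.550 - 1.96) = 34%; with d = 8 it gives Φ(0.980 - 1.96) = 16%.

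**Non-proportional hazards, median 12.**

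- Effect ends at month 12: uncensored -0.38; scenario (1) -0.38 by either handling; scenario (2) tied -0.41.
- Effect reverses after month 12 (log HR -0.7 per SD): uncensored -0.27; scenario (1) dropped -0.38 and last follow-up about -0.30; scenario (2) tied -0.40.

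The direction of bias is therefore not fixed. Across cuts the C-index itself runs from 0.63 to 0.68 in the first case and from 0.60 to 0.68 in the second.

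**The case against.** The strongest reply is that the plan intends follow-up to progression (B and C.6), and Section G adds that "the PI will work with the co-investigators and referring physicians to ensure that the patients continue to follow up as scheduled". The remark about likely non-progression refers to the end of a one-year funding period, whereas accrual runs for five years, so it does not show that non-progressors are expected at final analysis. This is fair, and nothing in the documents suggests that loss would depend on uptake. But these are commitments about follow-up. None ties the analysis to the last progression, and in scenario (1) complete progression is uncommon.

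Second, most of the harm comes from dropping non-progressors, which no section proposes. Last follow-up moves the correlation by only 0.01 to 0.04 in scenario (1), and tying at 12 months moves it by 0.03 to 0.09, well inside the sampling interval. This stands, and it is why the effect is called modest. It does not say which handling will be used.

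Third, the plan already names Kaplan-Meier and 6- and 12-month progression-free survival. That is a partial route, but Section E does not connect Fisher's test to those time points. Caution about a log-rank p-value is reasonable given its power, and that caution belongs to how the result is interpreted.

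Fourth, every magnitude rests on assumed inputs, and the longer medians lie close to the 18-month median survival. That is true of the size of the effect; the omission itself does not depend on them.

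**Conclusion.** The concern holds. The plan's main description of Objective 2 cannot accommodate patients who have not progressed, no data cut or rule is stated, and the only censoring-aware method is left in doubt. Under the assumed model, the handling chosen moves the mean correlation at median 12 from -0.41 to -0.15 at a 12-month cut, and from -0.44 to -0.33 with 12 to 72 months of follow-up, against -0.47 uncensored. There is no bias if all patients progress before analysis, and little with last-follow-up coding in the assumed setting.

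Confidence is high for the omission and lower for its size, which depends on the assumed hazard ratio, medians and cut. This is not a criticism of power: the aim is secondary and descriptive in a pilot that declares itself unpowered. It should be fixed because the remedy is cheap.

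**What to change.** Amend Section E as follows.

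- State the data cut and the time origin for progression-free survival. C.6 gives an origin only for time to PSA progression. Censor non-progressors at last follow-up as of that cut, and say which assessment counts as last follow-up.
- Make a censored-data concordance index, or a Cox hazard ratio on continuous uptake, with 95% CI, the main description of Objective 2.
- Always report Kaplan-Meier curves by median uptake. Label log-rank as descriptive and low in power, and delete the remark on feasibility.
- Apply Fisher's test to 6- and 12-month progression-free status.
- Keep Spearman as descriptive only: when all patients have progressed, or with non-progressors tied at a common 12-month cut under complete 12-month follow-up. Label the latter as describing the first 12 months.

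The cost is analysis wording, with no extra patients, visits or data. The measures will be imprecise. At median 12 with 12 to 72 months of follow-up, a Cox HR of 2 with standard error 0.33 has a 95% CI of exp(0.693 ± 1.96 × 0.33), about 1.05 to 3.8, and the C-index has a standard deviation of about 0.08. Fisher's test has about 17% power at 12 months and 10% at 6 months. The Cox and concordance measures also assume that loss is unrelated to prognosis given uptake, and under non-proportional hazards they depend on the cut. The cut must therefore be stated whichever measure is used.

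### Section E has no rule for non-progressors in its Spearman analysis, no analysis that keeps uptake continuous and handles censoring, and no patient-level uptake value; a one-covariate Cox model on a pre-named measure would be a cheap addition

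*Combined protocol and SAP*

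**What the plan says.** The protocol and SAP are one document. Section E lists these analyses of uptake against outcome:

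- A plot of uptake against time to progression, for which "the association will be described by Spearman correlation coefficient with 95% confidence interval (CI").
- A split: "we will dichotomize degree of uptake by median and define it as high vs. low", after which the plan will "apply Wilcoxon rank sum test or Fisher exact test wherever appropriate".
- A survival analysis: "The association with progression free survival will be able to describe by Kaplan-Meier method along log-rank p-value", followed by a caution that the small sample may rule it out. The sentence names no groups.

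Section E adds that this is a pilot and that no power can be claimed.

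On follow-up, Section B expects some patients to progress only after the funding period. Section C promises at least one year. C.6 says "We will utilize 6 and 12 month progression free survival outcomes and patients will be consented to be followed until there is any evidence", the event in question being progression. C.7 says "Accrual goals will be 4 patients every year for a total of 20 patients in 5 years".

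On uptake, C.5 works at lesion level: up to five index lesions per (unnamed) category, with SUVmax and SUVmean, and total lesion activity available. Its grades also apply to lesions: "a diagnosis of high Ga-68 DOTATATE uptake will be assigned to lesions with a SUVmax ≥ 8".

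**The concern.** Three gaps meet in one analysis.

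1. Spearman has no means of handling censoring, and Section E gives no rule for patients without progression. Read literally, a correlation with time to progression could be run on progressors only.
2. The hypothesis in Section B is graded: higher uptake, shorter time to progression. Yet the only censoring-aware method apparently uses the median split, which discards information and whose cut-point depends on who enrols. Its high group is also not the high grade of C.5.
3. Every analysis needs one uptake value per patient, and none is defined. The choice of maximum, mean or total, and of SUVmax or SUVmean, is left open until after the data are seen.

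The opening summary says the results may be used to design larger studies. A correlation of uncertain construction and a sample-specific cut are hard to carry forward; an HR per doubling of a named measure is easier.

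**Working it through.** **No plan figure to reproduce.** The documents give n = 20 but no effect size, event count, alpha or median PFS. Assumed here: two-sided 5%, exponential PFS, log-hazard linear in a standard-normal uptake measure. The main case is HR 2 per SD and median PFS 12 months.

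**Patients without a progression time at 12 months.** The progression-free fraction is 0.5^(12/m) for median PFS m.
- m = 9: 0.40, about 8 of 20.
- m = 12: 0.50, 10 of 20.
- m = 18: 0.63, about 13 of 20. This is a generous upper end, since Section G gives a median survival of 18 months.

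**What the missing rule does to Spearman (main case, mean rho).**

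| Handling | 12-month cut | Follow-up uniform 12–36 months |
|---|---|---|
| No censoring | -0.47 to -0.48 | -0.47 |
| Censored times kept as observed | -0.41 to -0.42 | -0.43 |
| Progressors only | -0.17 | -0.27 |

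At the 12-month cut, Spearman on progressors only rejects in 9% of trials, against 47% with censored times kept.

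**Comparison of methods (main case, rejection rate).** The accrual column uses uniform entry over 5 years (C.7) plus at least 12 months of follow-up (Section C).

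| | 12-month cut | 24-month cut | Accrual |
|---|---|---|---|
| Mean events | 10.3 | 14.4 | 16.4 |
| Cox, continuous uptake (score test) | 53% | 65% | 67% |
| Spearman, censored times kept | 47% | 56% | 54% |
| Median-split log-rank | 35% | 44% | 46% |
| Median-split Wilcoxon | 30% | 37% | 36% |

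- Cox minus Spearman: 53-47 = 6, 65-56 = 9, 67-54 = 13 points.
- Cox minus split log-rank: 53-35 = 18, 65-44 = 21, 67-46 = 21 points.
- Over HR 1.5 to 2.5 and median PFS 9 to 18 months, Cox leads Spearman by 2 to 14 points and the split log-rank by 6 to 23.
- Type I error: Cox 5.6–6.1%, log-rank 5.2–6.3%, Spearman 4.9–5.4%. With each test calibrated to 5%, Cox against Spearman is 50 v 46, 62 v 56 and 64 v 54%, so the gain is 4, 6 and 10 points.

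**Step effects.** With HR 3 exactly at the median, the split log-rank wins: 40–57% against 28–38% for Cox. With HR 3 in the top 42% (Section A cites 79 of 187 patients with neuroendocrine differentiation; 79/187 = 0.42), calibrated power over the three follow-up patterns is Cox 27/32/32%, Spearman 28/33/31%, log-rank 27/34/33%: no material difference.

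**Precision.**
- For a sample rho of magnitude 0.5 at n = 20, the 95% CI is tanh(0.549 ± 1.96 × 1.03/√17), or 0.06 to 0.78, before any censoring.
- For Cox, 80% power needs HR per SD = exp(2.80/√D): 2.43 at D = 10 events, 2.11 at 14, 1.87 at 20.
- With true HR 2 per SD, 95% of Cox estimates fall in 1.03–6.3 (12-month cut) or 1.14–4.9 (accrual).

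**Cut-point and patient value.**
- The median of 20 falls between the 30th and 70th population percentiles (95% range).
- With assumed within-patient lesion correlation 0.3–0.7 and 1 to 5, 10 or 15 lesions per patient, using the maximum instead of the mean moves 2.4–4.5 of 20 patients across the median on average. No patient moves in only 2–17% of trials.

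**The case against.** The strongest reply is that this is a declared feasibility pilot without power, that patients are followed to progression, and that the plan already lists Kaplan-Meier with log-rank. Much of that stands.

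- A reader might infer that the plan ignores censoring. It does not: the log-rank handles it, and 6- and 12-month PFS is known for anyone not lost early. What is missing is a rule within Spearman and a censoring-aware analysis of continuous uptake.
- A reader might infer that censoring is what makes Spearman weak. The figures say otherwise when censored times are kept: Cox leads least (6 points) where censoring is heaviest, and with no censoring at all it is still 73% against 59%. The gain comes mainly from the assumed log-linear truth. Only the progressors-only reading does serious damage.
- A reader might infer that Cox is better whatever the truth. The hypothesis in Section B can also be read as a distinct subset with presumed neuroendocrine disease, and under a step effect the advantage disappears or reverses.
- Patients with no visible focus do not defeat the planned rank methods; they can be tied lowest. It is a log-scale measure that needs a number for them.
- The above-liver positivity rule in Section C and the liver and/or SUV grading in C.5 serve different purposes. The wording could be aligned, but the documents do not make it an error.

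Follow-up to progression would largely dispose of the Spearman point if every patient reached an event. It would not define the patient-level measure or make up for the information lost in the split.

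**Conclusion.** The point holds as a moderate improvement to the secondary objective. Section E leaves non-progressors unaddressed in Spearman, has no analysis that is both continuous in uptake and censoring-aware, and leaves the patient-level uptake value open. The first gap is serious only if Spearman is run on progressors (mean rho about -0.17 instead of -0.48 at a 12-month cut). A Cox model gains about 6 to 13 points over Spearman and 18 to 21 over the split log-rank under a log-linear effect of HR 2 per SD and median PFS 12 months, part of it from a slightly liberal score test. Under a step effect it gains little or nothing, and it loses if the step is at the median. The HRs, median PFS, lesion correlation and lesion counts are assumptions, not figures from the documents. Cox does not make the study powered, and its HR will be imprecise at n = 20.

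**What to change.** In C.5 and Section E:

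1. Pre-name one patient-level measure, for example hottest-lesion SUVmax or its ratio to liver. Where no focus is visible, take the value at metastases known from baseline imaging that lie in the scanned field.
2. Add a one-covariate Cox model for PFS on log2 of that measure, with non-progressors censored at last assessment. Report the HR per doubling with 95% CI as an estimate, not a powered test.
3. Repeat it with the mean over index lesions as a sensitivity analysis, and report the number of lesions measured. A maximum rises with lesion count: if count alone drove PFS (assumed HR 2 per SD of count), Cox on the maximum would reject in 9–14% of trials and on the mean in about 6%.
4. Keep Spearman, never restricted to progressors, and the split, relabelled *above/below median*, as descriptive.

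The cost is a few sentences and some extra region-of-interest measurements on scans already acquired, with no added patients or visits. The downsides are the log-linearity assumption, which 20 patients can hardly check, a test size near 6%, and known metastases outside the scanned field that cannot be measured.

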Rationale. As has been outlined in Section A of this proposal, there is no established noninvasive imaging or laboratory technique to identify neuroendocrine transdifferentiation in prostate cancer (NEPC). Our hypothesis is that interrogating the upregulation of the somatostatin receptor which occurs within a subset of prostate cancer patients, or prostate cancer metastatic lesions, is possible by utilizing ⁶⁸Ga-DOTATATE PET as a visual biomarker, which specifically binds to the somatostatin receptor SSTR2 (the somatostatin receptor most upregulated in NEPC) (36). To that end we will perform ⁶⁸Ga-DOTATATE PET imaging on up to 20 patients to determine the degree of uptake in patients with metastatic prostate cancer (mCRPC) who is about the start first line of treatment (abiraterone acetate or enzalutamide) for castration resistant disease. We believe that this inflection point best balances early detection of potential neuroendocrine transdifferentiation with imaging, as these patients typically have higher ECOG (Eastern Cooperative Oncology Group) performance status than those further along the continuum of their treatment. Patients with mCRPC will continue to receive standard of care therapy with no clinical decisions being made based upon the results of the ⁶⁸Ga-DOTATATE PET study. The goal of this study is not to compare the diagnostic performance of ⁶⁸Ga-DOTATATE in neuroendocrine tumors with other imaging modalities, as this has already been externally verified (39-41).

Our hypothesis is that patients with higher levels of ⁶⁸Ga-DOTATATE uptake on an initial PET scan (presumed NEPC) will have a shorter time to progression while on oral agents (abiraterone acetate or enzalutamide) due to inherent resistance to antiandrogen based therapeutics (42) when compared to those with lower ⁶⁸Ga-DOTATATE uptake.

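### The high versus low uptake comparison has no planned effect estimate or interval; if Fisher's exact test is used for 6- and 12-month progression, it may yield only a p-value from a conservative test

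*Combined protocol and SAP*

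**What the plan says.** Section E (Statistical Analysis) forms two groups: "we will dichotomize degree of uptake by median and define it as high vs. low". It will then "apply Wilcoxon rank sum test or Fisher exact test wherever appropriate". It does not say which outcome goes with which test, and it gives no alpha, no sidedness, and no effect measure or interval for the two groups.

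Section C.6 supplies the outcome that Fisher's test would most naturally fit: "We will utilize 6 and 12 month progression free survival outcomes". Progression status at a fixed time is binary.

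Section E also plans two other descriptions. For uptake against time to progression, "the association will be described by Spearman correlation coefficient with 95% confidence interval (CI"). Progression-free survival is to be described by Kaplan-Meier with a log-rank p-value, with a caution that the small sample may make this infeasible.

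On size, Section C says "We will undertake a study with 20 patients who have castration resistant metastatic prostate carcinoma", while the rationale in Section B speaks of "imaging on up to 20 patients to determine the degree of uptake". Section E closes by saying that "no statistical power is possible".

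**The concern.** The opening summary says that the results may feed the design of larger studies. A designer needs the difference in 6- and 12-month progression between high and low uptake, and how uncertain it is. Section E promises neither for the dichotomised comparison. If Kaplan-Meier is dropped as infeasible, the group comparison of 6- and 12-month status may come down to a p-value.

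That p-value would come from a test that is conservative at this size. The median split fixes the group sizes, but the number of patients who progress is random. Fisher's test conditions on that number as well. With so few patients the conditional distribution is coarse, and the attained error rate falls well below the nominal level. A sizeable difference could then be reported as non-significant and be misread as no association.

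**Working it through.** The documents give no power, alpha or rate, so there is no figure of theirs to reproduce.

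**Inputs**
- n = 20 (Section C), a ceiling in Section B.
- Median split (Section E), giving 10 versus 10 if all 20 are evaluable and there are no ties. This is derived, not stated.
- Outcome: progressed or not by 6 or 12 months (inferred from C.6).
- Two-sided 5%: assumed.
- Progression rates by group: assumed. The plan gives only the direction.

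**Formulas.** Let a and b be the progressors in the two groups of n1 and n2.
- Power(π1, π2) = sum over all tables (a, b) of Bin(a; n1, π1) × Bin(b; n2, π2) × [p(a, b) ≤ 0.05].
- Size = the maximum of the same sum over a common rate π1 = π2.
- Boschloo's p for a table = the maximum over a common rate of the probability of all tables with a Fisher p at least as small.

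**Size of Fisher's test at 10 versus 10.** The rejection probability given the total number of progressors is 0 for totals up to 4 or from 16. Otherwise it is as below, weighted by the Binomial(20, 0.5) probability of each total:

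| Total progressors | Weight | Conditional rejection | Product |
|---|---|---|---|
| 10 | 0.1762 | 0.0230 | 0.0041 |
| 9 or 11 | 2 × 0.1602 | 0.0055 | 0.0018 |
| 8 or 12 | 2 × 0.1201 | 0.0198 | 0.0048 |
| 7 or 13 | 2 × 0.0739 | 0.0031 | 0.0005 |
| 6 or 14 | 2 × 0.0370 | 0.0108 | 0.0008 |
| 5 or 15 | 2 × 0.0148 | 0.0325 | 0.0010 |

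The sum, before rounding the products, is 0.0128. This is the maximum over the common rate; at a common rate of 20% it is 0.0076. Boschloo's test has a maximum of 0.0422. Of the 121 possible tables Fisher rejects 34 and Boschloo 46. The 46 include all of Fisher's 34.

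**Power at 10 versus 10**

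| Assumed rates | Fisher | Boschloo | Gain (points) |
|---|---|---|---|
| 80% v 30% | 42.6% | 62.2% | 19.6 |
| 90% v 40% | 47.4% | 65.9% | 18.5 |
| 70% v 30% | 24.3% | 41.8% | 17.5 |
| 70% v 40% | 12.3% | 24.8% | 12.5 |
| 60% v 40% | 5% | 13% | 8 |

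**Sensitivity to the split, at 80% v 30%**

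| Split | Fisher size | Fisher power | Boschloo power | Gain (points) |
|---|---|---|---|---|
| 9 v 9 | 2.1% | 43.8% | 52.9% | 9.1 |
| 8 v 8 | 2.1% | 40.4% | 42.9% | 2.5 |
| 8 v 9 | 3.4% | 48.4% | 48.4% or 56.3% | 0 to 8 |

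At 8 versus 9 the first Boschloo figure doubles the smaller one-sided p-value, and the second orders tables by the two-sided Fisher p. The gain was not negative in any split checked.

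**What an interval adds.** Take 8/10 versus 4/10, a difference of 0.40. The Wilson limits are 0.490 to 0.943 and 0.168 to 0.687. Newcombe's limits are then:
- lower: 0.40 − √[(0.800 − 0.490)² + (0.687 − 0.400)²] = 0.40 − 0.42 = −0.02
- upper: 0.40 + √[(0.943 − 0.800)² + (0.400 − 0.168)²] = 0.40 + 0.27 = 0.67

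For 8/10 versus 3/10 Fisher gives p = 0.070 and Boschloo p = 0.041. The difference is 50 points, 95% CI 7 to 74. The interval tells a planner more than either p-value.

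**The case against.** The strongest reply is that Fisher's test is valid at every sample size and that its conservatism cannot create a false positive. Conditioning on the margins is a defensible position. The plan is a feasibility pilot that disclaims power, progression is its secondary objective, and no decision is tied to this p-value. All of that stands, and it is why the interval should lead and the change of test come second.

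Three stronger readings are tempting, and the documents support none of them.

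- *Fisher runs at about 1% in place of a planned 5%.* The plan sets no alpha and does not name the outcome for Fisher's test. At a one-sided 5% level and 10 versus 10, Fisher's size is 2.1% and the gain at 80% versus 30% is 11 points.
- *The trial would recover 20 points of power.* That needs exactly 10 versus 10, every status known and an assumed difference of about 50 points. Section B allows fewer than 20 patients, and Sections C.4, C.6 and C.7 leave the timing of visits and much of the follow-up imaging and testing to the clinician, so some unknown statuses are likely.
- *A p-value would be the plan's only statement on progression.* Section E also plans a Spearman coefficient with a 95% confidence interval, and Kaplan-Meier if feasible. The gap concerns the high versus low comparison only, and the Wilcoxon option does not share Fisher's conservatism.

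It is also fair to say that Boschloo's two-sided p-value is not uniquely defined for unequal groups, so the convention has to be written down.

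**Conclusion.** The point holds as a cheap improvement. Section E plans no effect estimate or interval for high versus low uptake, and if Fisher's test is used for 6- and 12-month status, that comparison may report only a conservative p-value. Under an assumed two-sided 5% level and exactly 10 versus 10, the maximum true size is 1.3% for Fisher and 4.2% for Boschloo, and power at an assumed 80% versus 30% is 43% and 62%. The size of the gain depends on the split: it may be a few points or none once patients are lost or tied at the median. For a 20-point difference neither test is informative.

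A reader might infer that Fisher's test is a mistake here. It is not: it holds its level, and the plan's own wording leaves the choice of test open. Nor does either test deal with patients censored before 6 or 12 months. That is a separate question.

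**What to change.** In Section E, for progression status at 6 and 12 months by uptake group:

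1. Name this as the binary outcome. Report the difference in proportions with a 95% confidence interval (for example Newcombe's) as the main result.
2. State that a p-value above 0.05 will not be read as absence of association.
3. Where a p-value is given, use Boschloo's unconditional exact test in place of Fisher's. State alpha, that the test is two-sided, and which two-sided convention applies when the groups are unequal.

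The cost is a change of wording and the use of standard software. It needs no extra patients or visits, and the type I error stays below the chosen level. The downside is a test that some readers will not know. If the investigators prefer to keep Fisher's test, items 1 and 2 still carry most of the benefit.
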